1.3.3 TOXICOLOGY, SAFETY PHARMACOLOGY AND GENOTOXICITY

Toxicology studies:

In the pivotal 4-week Good Laboratory Practice (GLP) rat toxicity study [Study 8400256], the following treatment groups were compared to the control group: STP1 at 100:10 or 50:5 mg/kg twice a day [REDACTED]. The main findings of this study were decreased body weight gain and food consumption, minor clinical pathology changes and high liver weight associated with centro-lobular hepatocyte hypertrophy. This later finding was likely an adaptive mechanism in the rats. Most of these findings were reversible, were clinically silent and not considered adverse. Thus, STP1 at 100/10 mg [REDACTED] was considered the no observed adverse effect level (NOAEL) in the rats. This dose corresponds to a 100-fold safety margin for a human dose of 10 mg twice a day of [REDACTED] and of 1 mg twice a day of [REDACTED] based on allometric scaling.

In the pivotal 4-week GLP dog toxicity study [Study 01405001], the following once daily treatments were compared to the control group: STP1 at 8:0.8, 6:0.6 and 3:0.3 mg/kg/day [REDACTED]. The primary findings were emesis, decreased food consumption and body weight gain, suspected moderate dehydration and minor clinical pathology changes. Most of these findings were reversible. The primary target organ at necropsy was the kidney where minimal to

moderate degeneration/regeneration was noted at all STP1 dose levels. These histology changes were not observed at the end of the recovery period but resulted in minimal to mild interstitial fibrosis. As moderate tubular degeneration/regeneration was considered adverse, which was found in females in the low dose group, a NOAEL could not be determined for females. Therefore, the NOAEL was considered to be 3/0.3 mg/kg/day STP1 (████████) in male dogs only. This dose corresponds to a 10-fold safety margin for a human dose of 10 mg twice a day of █████ and to a 5-fold safety margin for a human dose of 1 mg twice a day of █████ based on allometric scaling.

Safety pharmacology studies:

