3.1.2 STOPPING RULES

Study Stopping rules

During and after the administration of STP1, the patient will be closely monitored for clinically significant signs and symptoms potentially related to the study drugs (ibudilast and bumetanide), in particular for signs and symptoms GI and dehydration and for clinically significant changes in the electrocardiogram (ECG). Any AE should be followed up until resolution. If not resolved, STALICLA shall be contacted and the patient may be considered to withdrawn from the trial depending on the severity of the event/s.

The DSMB will perform reviews of safety data throughout the study.

Enrolment in the study will be placed on hold and no further dosing will occur pending a full safety review if:

- One fatal or life-threatening SAE occurs, that is considered by the investigator as potentially or possibly related to SPT1 and later confirmed the patient received investigational medicinal product (IMP).
- STALICLA, investigators and/or the DSMB considers that the number and/or severity of AEs, abnormal safety monitoring tests or abnormal laboratory findings justify putting the study on hold. Examples are:
 - One severe systemic-related reaction occurs and does not resolve within 24 hours.
 - Three or more similar severe AEs occur as defined by the Common Terminology Criteria for Adverse Events (CTCAE v5.0), which are judged related to STP1.

- If 2 patients at any dose level discontinue treatment due to changes in vital signs, ECG intervals or findings on continuous ECG monitoring no further patients will be enrolled at this dose level pending review by DSMB.

The DSMB can recommend (i) for the study to continue without amendment, (ii) to continue the study with modifications to the protocol or (iii) to stop the study.

The study may continue after the safety review, if the DSMB and STALICLA agree it is safe to proceed.

Individual stopping rules

If a patient experiences an AE following administration of study drug (i.e., post-treatment) that is judged to be related to the study drug, and is graded as severe or SAE, no further doses of study drug will be administered.

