- ECG and vital signs data (including orthostatic blood pressure changes).
- Data quality, completeness and timeliness.
- Adherence to the protocol.

The DSMB will specifically assess the changes from baseline all safety laboratory data with a more specific evaluation of potential electrolyte imbalance and coagulation parameters.

The DSMB will provide recommendations to STALICLA as to whether the study should continue according to the protocol (i.e., proceeding with the recruitment for the second dose level of [REDACTED] mg twice a day (6 hours apart) of [REDACTED] mg twice a day (6 hours apart) of [REDACTED]) or be terminated.

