5.1.3 ADVERSE EVENTS OF SPECIAL INTEREST (IMMEDIATELY REPORTABLE TO THE SPONSOR)

AESIs are required to be reported by the investigator to the sponsor immediately (i.e., no more than 24 hours after learning of the event; see [Section 5.4.2](#) for reporting instructions). AESIs for this study include the following:

- Electrolyte imbalance: hypokalemia (K⁺ level <3.4 mEq/L), hyperkalemia (>5.0 mEq/L), hyponatremia (Na⁺ level <135 mEq/L), hypochloremia (Cl⁻ level <97 mEq/L)
- Thrombocytopenia is defined as meeting one or both criteria:
 - Platelet count below $150 \times 10^9/L$ (or 150.000 platelets per microliter (mcL))
 - Platelet count drop of $\geq 50\%$ compared to baseline
- Drug-induced liver injury (DILI)
- Dehydration and orthostasis (defined by a fall in systolic blood pressure over 20 mm Hg or a fall in diastolic pressure over 10 mm Hg within 3 minutes of standing).

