5.2 SAFETY PLAN

The Safety Plan considers observations made in non-clinical investigations including GLP toxicology studies in rats and dogs and the observations made in clinical trials. Hypothetical considerations are included in the interpretation of non-clinical and clinical data.

The safety monitoring and the frequency of the scheduled visits are described in [Appendix 1](#). All safety data will be reviewed throughout the study by the sponsor in a treatment-blinded manner. However, the DSMB will review the blinded safety and tolerability data obtained from the first dose cohort (8 patients) who finish the 2 weeks of treatment and the 2 weeks of follow-up. The following sections specify some of the monitoring measures that will be taken to maximize the patient's safety in this study.

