5.2.1 MANAGEMENT OF SPECIFIC ADVERSE EVENTS

5.2.1.1 ABNORMAL LABORATORY FINDINGS

Laboratory abnormalities reported with [REDACTED] included hyperuricemia (18.4%) and electrolytes imbalance (e.g., hypochloremia for 14.9% or hypokalemia for 14.7%). Hypokalemia was also observed in a [REDACTED] dose-dependent manner in the BUMEA trial [NCT01078714; Lemonnier et al, 2017]. In the current study, laboratory assessment will be done every week during the treatment period and at the end of the follow-up period. If hypokalemia is observed, potassium supplements should be administered, and patients should be advised to eat potassium-rich foods.

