5.3.5.4 ABNORMAL LABORATORY VALUES

Not every laboratory abnormality qualifies as an AE. A laboratory test result should be reported as an AE if it meets any of the following criteria:

- Accompanied by clinical symptoms.
- Results in a change in study treatment (e.g., dosage modification, treatment interruption, or treatment discontinuation).
- Results in a medical intervention (e.g., potassium supplementation for hypokalemia) or a change in concomitant therapy.
- Clinically significant in the investigator's judgment.

It is the investigator's responsibility to review all laboratory findings. Medical and scientific judgment should be exercised in deciding whether an isolated laboratory abnormality should be classified as an AE.

If a clinically significant laboratory abnormality is a sign of a disease or syndrome (e.g., ALP and bilirubin 5 times the upper limit of normal (ULN) associated with cholecystitis), only the diagnosis (i.e., cholecystitis) should be recorded on the AE eCRF page.

If a clinically significant laboratory abnormality is not a sign of a disease or syndrome, the abnormality itself should be recorded on the AE eCRF page, along with a descriptor indicating if the test result is above or below the normal range (e.g., "elevated potassium", as opposed to "abnormal potassium"). If the laboratory abnormality can be characterized by a precise clinical term per standard definitions, the clinical term should be recorded as the AE. For example, a serum potassium level of 7.0 mEq/L should be recorded as "hyperkalemia".

Observations of the same clinically significant laboratory abnormality from visit to visit should not be repeatedly recorded on the AE eCRF page, unless the etiology changes. The initial severity of the event should be recorded, and the severity or seriousness should be updated any time the event worsens.

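### The kidney was the target organ in dogs, but no adverse event of special interest covers it, so a non-serious creatinine rise has no baseline-relative trigger and needs no 24-hour report

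*Protocol*

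**What the plan says.** **The animal finding.** Protocol 1.3.3, on the 4-week GLP dog study: "The primary target organ at necropsy was the kidney". Tubular change was seen at every STP1 dose. After recovery, minimal to mild interstitial fibrosis remained. Moderate tubular change was considered adverse, "which was found in females in the low dose group, a NOAEL could not be determined for females". The NOAEL of 3/0.3 mg/kg/day therefore applies to male dogs only. The trial enrols both sexes (4.2.2).

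**The AESI list.** Section 5.1.3 opens with "AESIs for this study include the following" and gives four groups, repeated in the synopsis:
- electrolyte imbalance, with numerical limits
- thrombocytopenia, by an absolute count or a fall of at least 50% from baseline
- drug-induced liver injury
- dehydration and orthostasis

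**Reporting.** Section 5.4 requires a 24-hour report for SAEs, AESIs and pregnancies. Section 5.3.5.4 says "Not every laboratory abnormality qualifies as an AE". A result counts if it brings symptoms, a change in study treatment or a medical intervention, or if the investigator considers it clinically significant.

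**Review.** Section 3.1.3 has the DSMB assess "changes from baseline all safety laboratory data with a more specific evaluation of potential electrolyte imbalance and coagulation parameters" before the dose is raised. Sections 3.1.3 and 5.2 also provide for continuing blinded review of safety data by the sponsor. Under 3.1.2 the study can be held if it is considered that "abnormal safety monitoring tests or abnormal laboratory findings justify putting the study on hold".

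**The concern.** The AESI list decides which findings must reach the sponsor at once, whatever the investigator thinks of their importance. In this protocol it is not confined to likely events. Section 1.5.2 says thrombocytopenia is not expected at these doses, yet platelets have an AESI with a baseline-relative criterion, a discontinuation criterion (3.1.2) and a per-patient plot (SAP 4.2). The organ that showed an adverse lesion at the lowest dog dose has none of these. Section 5.2 states "The Safety Plan considers observations made in non-clinical investigations including GLP toxicology studies in rats and dogs", but its specific subsections deal with electrolytes, blood pressure and suicidality.

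At stake is the speed and certainty with which an early renal signal reaches the sponsor in the first human use of the combination, in a study whose second cohort doubles the ibudilast dose from 5 to 10 mg twice a day (3.2.1). On the face of 5.1.3, a potassium of 3.3 mEq/L is an AESI, because it lies below 3.4. A non-serious doubling of creatinine is not.

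**Working it through.** **1. The paths open to a non-serious creatinine rise**

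| Step | Source | Platelets or electrolytes | Creatinine |
|---|---|---|---|
| Measured at screening, Days 7, 14, 28 | Protocol 4.6.1.5, Appendix 1 | yes | yes |
| Preset criterion | Protocol 5.1.3 | yes; platelets also relative to baseline | none |
| 24-hour report if not serious | Protocol 5.4 | yes, as an AESI | no |
| Recorded as an AE | Protocol 5.3.5.4 | symptoms, action taken or investigator's opinion | same |
| Flag in patient listings | Protocol 6.4.2; SAP Data Listings 7 and 9 | outside normal range | outside normal range |
| Normal/high/low shift table and out-of-range counts | SAP 4.2 | electrolytes only | no |
| Per-patient plot | SAP 4.2 | yes | no |
| DSMB change from baseline | Protocol 3.1.3 | yes | yes, with all safety laboratory data |

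Suppose creatinine rises but stays within the normal range, without symptoms, and the investigator does not consider it significant. The values appear in Data Listing 7, but that listing has no change-from-baseline column and would not flag them. No rule sends them to the sponsor at once.

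**2. How much data the escalation review holds**

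The first cohort has 8 patients, 6 of them active, with three post-baseline chemistry visits:
- 8 × 3 = 24 scheduled creatinine values
- 6 × 3 = 18 from active patients, of which 6 × 2 = 12 fall on Days 7 and 14

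The serum creatinine paired with the PK urine collections may add a few.

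**3. What a renal AESI would cost in chance reports**

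The plan's maximum enrolment reproduces: 16 / (1 − 0.20) = 20. The within-person CV of creatinine is not in the documents and is assumed to be 5%, 10% or 15%. Assume log-normal values, no true change, one screening baseline shared by three later visits, and a trigger at k times baseline. With s = √ln(1 + CV²), the chance per patient of at least one trigger is

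P = ∫ φ(b) · [1 − Φ((ln k + s·b)/s)³] db.

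| k | CV | s | P per patient | Expected in 8 | Expected in 20 |
|---|---|---|---|---|---|
| 1.5 | 5% | 0.050 | 1.4 × 10⁻⁸ | 0 | 0 |
| 1.5 | 10% | 0.100 | 0.0057 | 0.05 | 0.11 |
| 1.5 | 15% | 0.149 | 0.068 | 0.54 | 1.36 |
| 1.3 | 10% | 0.100 | 0.078 | 0.62 | 1.55 |

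A trigger at 1.5 times baseline gives few chance reports over this range. At 1.3 times and a CV of 10% there would already be about 1.6 in 20 patients.

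**The case against.** The best case against the point is that renal function is well covered already:
- Creatinine, urea and urinalysis are scheduled throughout, and the sponsor reviews safety data blinded as the study runs.
- The investigator must review every laboratory result (5.3.5.4). Unexplained clinically significant values are repeated at once and followed (4.6.1.5).
- The investigator can class an event as medically significant, which makes it an SAE with a 24-hour report (5.1.2).
- Renal disease is excluded at entry (4.2.3), and dehydration and orthostasis are already an AESI and a discontinuation criterion.
- The choice of AESIs is the sponsor's, and the amendment summaries show two changes to the list at FDA's request.
- The dog finding was a histological lesion with minor clinical pathology changes. Nothing in the documents shows that a creatinine of 1.5 times baseline would detect its human counterpart.

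Most of this stands, and it limits the point to reporting speed and the lack of a preset criterion. It does not remove it, because every step before the DSMB review depends on the normal range or on someone's opinion. The limited sensitivity of creatinine is a fair caution about what the trigger can achieve, but creatinine is the renal marker that the study already collects.

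A reader might infer that the kidney goes unexamined before escalation. The documents do not support that. Section 3.1.3 commits the DSMB to change from baseline in all safety laboratory data, and creatinine and urea are in that panel. Electrolytes and coagulation merely receive added emphasis. The Interim Analysis Plan named in SAP 2.4 was not available and may contain renal displays.

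A reader might also rely on the two dog safety margins in 1.3.3, 10-fold and 5-fold. They cannot both hold at 10 mg and 1 mg twice a day, since 3/20 = 0.3/2 = 0.15. Which figure or dose is the slip cannot be settled from the text. Section 1.5.2 already works with 5-fold, so this is not a ground for the point.

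**Conclusion.** The point holds in a limited form. The kidney was the dog target organ with no female NOAEL, and no AESI covers it. A non-serious creatinine rise therefore has no baseline-relative trigger and no 24-hour report, unlike platelet or electrolyte changes. This is a cheap improvement to patient safety, not the repair of an unmonitored risk.

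The documents allow no estimate of how many renal events would be reported late, so the size of the benefit is unknown. Only the cost can be quantified: about 0 to 1.4 chance reports in up to 20 patients at 1.5 times baseline. That figure rests on an assumed within-person CV of 5% to 15%, log-normal values, a single screening baseline and three later visits. Reports of true diuretic-related rises would be additional.

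**What to change.** In Protocol 5.1.3 and the matching synopsis list, add a renal AESI in the same form as the platelet criterion: serum creatinine at or above a stated multiple of the screening value, for example 1.5 times. The multiple is an assumption, and the sponsor should confirm it. Screening is the right reference because SAP 4.2 uses it as the laboratory baseline and no safety chemistry is scheduled on Day 1.

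The cost is one line in two places. It needs no new sample, visit or table, since SAP Tables 11 and 12 and Data Listing 3 already report AESIs. The burden is the small number of extra 24-hour reports estimated above.

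Optionally, name creatinine, urea and urinalysis beside electrolytes and coagulation in 3.1.3. This only adds emphasis to a review already promised, and becomes a cross-reference if the Interim Analysis Plan has a renal display. No renal stopping criterion is needed: under 3.1.2, drug-related severe AEs and SAEs already end dosing, and abnormal laboratory findings can already lead to a hold.

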1.4 PREVIOUS CLINICAL EXPERIENCE

At the time of writing, STP1 has not been investigated clinically and [Study STP1-C004](#) is the first in-human study. However, both compounds have been developed for different indications and safety and pharmacokinetic data have been published for both compounds.

[REDACTED] has been marketed in 10-mg capsules by [REDACTED] for the treatment of [REDACTED]

[REDACTED] is a loop diuretic that has been marketed in the US [REDACTED]. It is prescribed for the treatment of [REDACTED]

[REDACTED]

In humans, the bioavailability of [REDACTED] is reported to range from 59 to 89% with a median value of about 80% [Brater, 1991]. Plasma protein binding of [REDACTED] is high (from 93 to 97%) [Turmen et al, 1982]. The observed [Tissue]/[Plasma] ratios for [REDACTED] are low including low brain levels after systemic administration [Löscher et al, 2013]. To date, the main enzymes responsible for [REDACTED] metabolism in humans have not been identified and described in the literature. The drug is rapidly eliminated by urinary excretion ($t_{1/2}$ between 1 and 1.5 hours), with approximately 80% of an oral dose of ^{14}C -labeled [REDACTED] in human volunteers recovered in urine and with 45% eliminated as unchanged drug. Approximately 2% of the administered dose is eliminated by biliary excretion, suggesting that liver biliary excretion plays a minor role in drug elimination [Burinex Product Monograph, 2018]. Results from in vitro experiments indicate that [REDACTED] is not expected to cause clinically relevant inhibition of cytochrome P450 in humans [Study 8400152]. After single oral dose of [REDACTED] in healthy volunteers, the T_{max} occurred between 0.5 and 2 hours post-dose, with mean C_{max} values between 31 and 48 ng/mL following 1 mg of oral [REDACTED] [Holazo et al, 1984; Yagi et al, 1999]. The $t_{1/2}$ ranged between 0.7 and 1.5 hours in the majority of studies following both oral or intravenous administration and the $AUC_{0 \infty}$ observed for oral doses of 1 and 2 mg were around 100 and 140 ng.h/mL.

Because [REDACTED] is a diuretic drug, it may have an effect on the renal clearance of [REDACTED] and could cause a reduction in its plasma level. Thus, urinary drug levels of [REDACTED] will be measured in this study.

1.4.2 SAFETY AND TOLERABILITY

There is no safety data from the administration of STP1 in humans, but it is available for each of its components.

[REDACTED]

From the clinical Japanese studies, the most common adverse events (AEs) recorded in approximatively 15,000 adult patients with either bronchial asthma or complications following cerebral infarction were anorexia (0.58%), nausea (0.56%) and increased liver enzyme levels (0.36%); rare cases of thrombocytopenia were also reported [REDACTED]. Ledeboer et al. have summarized the safety data from studies in asthma and post-stroke dizziness from Japanese articles [Ledeboer et al, 2007]. In a double-blind, placebo-controlled study of 238 patients with post-stroke dizziness, [REDACTED] given at 30 mg once daily for 8 weeks did not show AE differences compared with placebo. The most common AEs were GI effects (11.2%), including anorexia (4.3%) and hepatic dysfunction (4.3%). In a 2-

year, open-label study of the recurrence of stroke where [REDACTED] (N=937) was given at 30 mg/day, 2.3% showed GI effects; [REDACTED] was discontinued in 1.8% of the patients. More recently, [REDACTED] was tested at dosages up to 100 mg/day in patients with multiple sclerosis [Fox et al, 2018] or opioid abusers [Cooper et al, 2017]. [REDACTED] was well tolerated, with an increased incidence of either headache or GI effects (i.e., nausea, diarrhea) compared with placebo. Table 1 summarizes the published clinical studies with the most frequently reported AEs for [REDACTED]

[REDACTED]
[REDACTED] doses from 0.5 to 2 mg twice a day for up to 3 months were studied in two randomized, double-blind, placebo-controlled trials in children and adolescents (2 to 18 years old) with ASD [Lemonnier et al, 2012; Lemonnier et al, 2017]. The frequency of AEs was correlated with the [REDACTED] dose. The most frequent AEs were hypokalemia, increased diuresis, loss of appetite, dehydration and asthenia. Hypokalemia occurred mainly at the beginning of treatment with the 1.0 and 2.0 mg twice a day doses and improved gradually with oral potassium supplementation. The minimally effective and safe [REDACTED] dose in the treatment of ASD was [REDACTED] mg twice a day; however, a [REDACTED] dose of [REDACTED] mg twice a day for 6 months is currently being evaluated in ongoing confirmatory trials in pediatric subjects.

In this trial, a [REDACTED] mg dose twice a day will be given over 2 weeks and laboratory safety monitoring will be implemented. If needed, oral potassium supplementation will be provided.

AE=adverse event; BID=twice daily; CO=crossover; DB=double-blind; GI=gastrointestinal; HV = healthy volunteers; MAD=multiple ascending dose; MS=multiple sclerosis; N/A=not available; NCT=National Clinical Trial number OLE=open-labeled extension; PC=placebo-controlled; PI=principal investigator PK=pharmacokinetics; PD=pharmacodynamic; R=randomized; TID=three times daily; y=age.

1.5 STUDY RATIONALE AND BENEFIT-RISK ASSESSMENT

1.5.1 STUDY RATIONALE

ASD is characterized by a high heterogeneity in its behavioral manifestations matched, by very complex genetic underpinnings, suggesting the existence of subtypes of ASD. Therefore, efforts to categorize autism are still of critical importance and must rely on defining a relationship between clinical symptoms and biological mechanisms to improve on the outcome of clinical trials. STALICLA has identified a first subpopulation with idiopathic ASD (called ASD-Phen1) defined by clear clinical signs and symptoms that can be linked to dysregulation in key intracellular pathways and transcription factors as well as immune response dysregulations. The combination of ibudilast and bumetanide, called STP1, has been identified as the most promising drug candidate to modulate the identified dysregulations in ASD-Phen1 patients.

[REDACTED] is expected to be the main driver of the potential effect of STP1. Its anti-inflammatory effect as a PDE4 and PDE10 inhibitor should exert beneficial immunomodulatory, and cognitive and behavioral effects by regulating energy metabolism. [REDACTED] although not an ASD-Phen1-selective compound, has been identified as a relevant candidate to maintain the effect of [REDACTED] over time in this specific patient population. Promising results have confirmed the existence of such an ASD subpopulation at the cellular level (see Section 1.3.1). *In vitro*, ibudilast has demonstrated its potential to modulate the identified dysregulated pathways in ASD-Phen1 cell lines (for further information, please refer to the STP1 Investigator's Brochure [STP1-IB]). In addition, STP1 has shown a good safety profile in nonclinical toxicology studies. Taken individually, both compounds have also demonstrated good clinical safety and tolerability profiles over a broad range of doses and indications. The present 2-week treatment, 2-dose level study will assess for the first-time tolerability, safety and PK profiles of STP1 in adult individuals with ASD-Phen1. The study was designed as a randomized, double-blind, placebo-control, 2-dose, ascending study.

The use of a placebo-control arm allows for a fair comparison to assess safety, tolerability and potential pharmacodynamic (PD) effect of STP1.

Despite the amount of supporting clinical safety data available for both compounds (see Section 1.4.2), this is the first time that STP1 will be tested in humans. Therefore, a stepwise ascending dose approach was chosen, starting with a "low" dose of [REDACTED] mg twice a day (i.e., below the dose typically prescribed for other indications and at the lower range of the Concentration that gives half the maximum inhibition [IC_{50}] for PDE4). Once the first dose cohort (8 patients) finishes 2 weeks of treatment and 2 weeks of follow up, the Data Safety Monitoring Board (DSMB) will advise STALICLA whether the study can pursue with the second dose level of [REDACTED] mg twice a day [6 hours apart]). In order to obtain sufficient safety and tolerability data to support a Phase 2 trial with a similar or lower dose of [REDACTED] the dose of [REDACTED] will be kept at 1 mg twice a day in both cohorts.

